2.4 Sample size

This is a single centre study to be performed in patients attending the NHS National Barth Syndrome Service. A total of 18 males aged between six and 24 years currently attend the service. We anticipate that between 12 and 15 UK patients are likely to consent to take part.

In a simple crossover trial (a single intervention and control comparison), the standard deviation (SD) of the within subject difference between treatments is given as: square root of 2 times the within subject SD. In a crossover trial, all participants act as their own control.

In this trial, the difference in mean peak volume of O₂ consumption between placebo and bezafibrate phases will be tested, assuming a 2-tailed type I error of 5%. For a sample size of 12 participants, the trial will be able to detect a difference of 0.90 (within subject) SDs with 80% power, or 1.05 SDs with 90% power.

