4.4 Definition and derivation of the outcomes

4.4.1 Primary outcome

Peak VO₂ is defined as the peak oxygen consumption on bicycle ergometry at baseline and in the final week of each treatment period.

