4.5 Analysis of the outcomes

4.5.1 Primary outcome

Peak VO₂

Peak VO₂ (VO₂ max (ml/kg/min)) will be the primary analysis, and will be analysed formally using a mixed linear regression model to compare bezafibrate against placebo, adjusting for period as a fixed effect (exploring interactions where necessary) and participants as random effects. Nested models will be compared using the likelihood ratio test. Model assumptions will be tested using standard methods, including residual plots etc., and a test for carry-over will be carried out by including treatment sequence in the model. If these assumptions do not appear to be valid then alternative methods will be explored.

Rest VO₂ will also be analysed formally in a similar way to peak VO₂. Peak wattage achieved (when peak VO₂ is measured) will be assessed for consistency within participants across time periods by calculating the correlation.

Peak and rest VO₂, and 2 and 6 min recovery VO₂ will also be summarised descriptively using means and standard deviations (SDs) (or medians and interquartile ranges (IQRs) depending on the distribution) at each period separately, and graphical representations of the distribution will be presented by treatment and period.

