Cardiac function is measured by ECHO and MRI. The main ECHO parameters of interest reported at rest, exercise and 2 min recovery are:

- Left ventricular biplane ejection fraction (LVEF %)
- Left ventricular peak systolic mean longitudinal strain (LV PSMLS %)
- Left ventricular peak systolic mean circumferential strain (LV PSMCS %),
- Diastolic ratio (MV E / LV E' cm/s)

The main MRI parameters of interest at rest are:

- LVEF %

- Right ventricular ejection fraction (RVEF %)

All these parameters will be analysed formally using mixed linear regression models to compare bezafibrate against placebo, in the same way, using the same methods as the primary analysis of peak VO_2 above.

Other data collected relating to cardiac function will be summarised descriptively using means and standard deviations (SDs) (or medians and interquartile range (IQR) depending on the distribution) or counts and percentages (where appropriate) by treatment, period and overall and will include:

Cardiac function at rest:

- LV function
 - Fraction shortening (Teichholz) (%)
 - Biplane ejection fraction (%)
 - Myocardial performance index
 - Mitral annular plane systolic excursion (MAPSE) – lateral and septal (mm)
- LV Tissue Doppler
 - S', E' and A' wave velocity (cm/s)
 - IVA (m/s^2)
 - E/E'
 - Mean systolic longitudinal strain (%) and strain rate
 - Lateral basal, mid and apical (%)
 - Septal basal, mid and apical (%)
 - Mean systolic circumferential strain (%) and strain rate
 - Anterior septal, anterior, lateral, posterior, inferior, septal (%)
 - E and A wave velocity (cm/s)
 - Deceleration time (ms)
 - E/A
 - IVS S', E' and A' wave velocity (cm/s)
 - IVS IVA (m/s^2)
 - 3D mean systolic strain
 - Wall motion abnormalities (Yes, No) – including description
- RV function
 - Wall motion abnormalities (Yes, No) – including description
 - TR peak velocity (m/s) (if given)
 - TAPSE (mm)
 - Myocardial performance index
 - Fractional area of change (%)
 - Mean systolic longitudinal strain (%) and strain rate
 - Lateral basal, mid, and apical (%)
- RV Tissue Doppler (pulsed wave)
 - S', E' and A' wave velocity (cm/s)
 - IVA (m/s^2)
 - E/E'
 - E and A wave velocity (cm/s)

Cardiac function during exercise will also be summarised descriptively using means and SDs (or medians and IQRs) or counts and percentages (where appropriate) by treatment, period and overall and will include:

- Exercise history
 - Exercise (hr/week)
 - Self-assessment of exercise capacity (1 = Low, 10 = Elite)

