- Motivation (Low, Average, High)
- Exercise test
 - The following will be taken at: baseline (pre-exercise); at 20W increments starting at 0W until 160W; and in recovery (2 and 6 mins post-exercise)
 - Heart rate (bpm)
 - Systolic and diastolic blood pressure (mmHg)
 - Peripheral capillary oxygen saturation (SpO₂) (%)
 - Comments on symptoms and ECG
 - Near-infrared spectroscopy (NIRS) (%)

The following will also form part of the exercise test:

- Exercise duration (m:s)
- Achieved work rate
- Cause and comments on cessation
- Perceived exercise effort – Borg scale at end of exercise (1-10)
- Peak heart rate (bpm)
- Systolic and diastolic blood pressure at rest and peak (mmHg)
- Exercise ECHO
 - The following will be taken at: baseline (pre-exercise); at 20W increments starting at 0W until 160W; and in recovery (2 and 6 mins post-exercise)
 - MV E cm/s
 - LV PSMLS %
 - LV PSMCS %
 - LV S' cm/s
 - LV E' cm/s
 - RV PSMLS %
 - TR m/s
 - RV S' cm/s
 - RV E' cm/s

The following will also form part of the exercise ECHO:

- Anaerobic threshold (%)
- O₂ pulse (ml/beat)
- RER
- METs
- VO₂ measurement at baseline (pre-exercise) and at recovery (2 and 6 mins post-exercise) (ml/kg/min)

Cardiac function by ECG will be summarised descriptively using means and SDs (or medians and IQRs) or counts and percentages (where appropriate) by treatment, period and overall. ECG at rest will include:

- Heart rate (bpm)
- Baseline rhythm, status of the following:
 - Sinus rhythm
 - Heart block
 - Atrial fibrillation/flutter

- Paced
- P wave normal
- P-axis (°)
- PR-interval (ms)
- QRS-axis (°)
- QRS-duration (ms)
- Left ventricular hypertrophy
- Right ventricular hypertrophy
- ST-segments
- ST depression
- TWI
- T axis (°)
- QTc (ms)

ECG during exercise will report new rhythm (sinus rhythm, heart block, atrial fibrillation and pacing occurrence), if changed.

Cardiac MRI data will also be summarised descriptively using line listings, means and SDs (or medians and IQRs) or counts and percentages (where appropriate) by treatment, period and overall, and will include for both left and right ventricular function in turn:

- Existence of wall type abnormalities, and if so, what type and where
- Structure
- Absolute and indexed ventricular function:
 - Ejection fraction (%)
 - End diastolic volume (mL/m²)
 - End systolic volume (mL/m²)
 - Stroke volume (mL)
 - Cardiac output (L/min)
 - Cardiac index (L/min/m²)
 - Mass (g/m²)

Lymphocyte mitochondria

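### Within-participant consistency of peak wattage is judged by a correlation of unstated type, which measures association and not agreement and gives neither the size nor the direction of a shift

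*SAP*

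**What the plan says.** SAP section 4.5.1 sets out the mixed model for peak VO₂ and then adds a supporting check: the wattage reached when peak VO₂ is measured "will be assessed for consistency within participants across time periods by calculating the correlation". It does not say which coefficient is meant, what value would count as consistent, or what follows if the value is low. Under section 4.4.1 the exercise test takes place "at baseline and in the final week of each treatment period".

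Three other places bear on the point:

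- Section 2.4 describes the source population: "A total of 18 males aged between six and 24 years currently attend the service". The power statement is for 12 participants.
- Section 4.5.2 (cardiac function, exercise test) records measurements "at 20W increments starting at 0W until 160W". One stage is therefore 20 W.
- The same part of section 4.5.2 lists achieved work rate among the exercise variables to be summarised descriptively by treatment, by period and overall. It also lists motivation, Borg score, peak heart rate, cause of cessation and RER.

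**The concern.** The stated aim is consistency within participants: did each one reach about the same workload at each test? A correlation answers a different question, namely whether those who reached a high workload in one period also did so in the other. The two come apart when everyone moves together, or when participants differ so much from each other that their ordering survives sizeable individual changes.

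Peak VO₂ is the only primary outcome and depends on how far the participant exercises, so this check will colour how a treatment difference is read. A high coefficient invites the conclusion that the tests were comparable, whether or not they were. A lower one does not say how many watts were gained or lost, or on which treatment.

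**Working it through.** The SAP gives no figure for wattage consistency, so there is none of its own to reproduce.

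**Inputs.** From the SAP: 12 participants, ages six to 24, 20 W stages, two sequences allocated 1:1. Assumed, because the SAP gives no wattage SD: within-participant SD (SDw) 10 W, between-participant SD (SDb) 10 to 40 W, and a systematic shift d of up to 20 W (one stage).

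**1. No shift.** r = SDb² / (SDb² + SDw²).
- SDb 30: 900/1000 = 0.90
- SDb 40: 1600/1700 = 0.94

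**2. The same shift for everyone between periods.** Adding a constant to one variable changes neither its variance nor its covariance with the other, so Pearson's r is exactly unchanged. This needs no assumed SD. In 20,000 simulated trials of 12 participants, the median r was the same for period shifts of 0, 9 and 20 W: 0.91 at SDb 30 and 0.95 at SDb 40. Lin's concordance coefficient, which does measure agreement, fell with the 20 W shift from 0.89 to 0.73 and from 0.94 to 0.83 respectively.

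**3. A shift by treatment, sequences balanced.** Half the participants are lower in period 1 and half in period 2. This adds d²/4 to each variance and takes d²/4 from the covariance:

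r = (SDb² − d²/4) / (SDb² + SDw² + d²/4)

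| SDb (W) | d (W) | Calculation | r | r with no shift |
|---|---|---|---|---|
| 30 | 15 | 843.75/1056.25 | 0.80 | 0.90 |
| 30 | 20 | 800/1100 | 0.73 | 0.90 |
| 40 | 15 | 1543.75/1756.25 | 0.88 | 0.94 |
| 40 | 20 | 1500/1800 | 0.83 | 0.94 |
| 20 | 20 | 300/600 | 0.50 | 0.80 |
| 10 | 20 | 0/300 | 0.00 | 0.50 |

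The coefficient does fall, and falls further when the spread is smaller. Its value cannot be decoded, though: r = 0.80 arises at SDb 20 with no shift (400/500) and also at SDb 30 with a 15 W treatment shift.

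**4. Sampling variation at n = 12.** At SDb 30 the simulated interquartile range of r was 0.86 to 0.94 with no shift and 0.81 to 0.91 with a 9 W treatment shift. These overlap heavily.

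**5. What a difference would show.** The SD of a within-participant difference is √2 × 10 = 14.1 W. With 12 participants the 95% CI for the mean period difference is ± 2.201 × 14.1/√12 = ± 9.0 W (t on 11 df). A true 20 W shift would appear as about 20 W (11 to 29), with limits of agreement of ± 1.96 × 14.1 = ± 27.7 W around the mean, whatever the between-participant spread.

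**The case against.** Much can fairly be said for the plan as written.

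- **The SAP does look at wattage by treatment elsewhere.** A reader might infer from section 4.5.1 that it never does. That is not so: achieved work rate is to be summarised by treatment and period, and a mean shift of one stage could show there. This stands as partial mitigation. The summary gives no paired difference or confidence interval and is not tied to the consistency check.
- **A treatment shift does move the coefficient.** A reader might infer that r is blind to any shift. That holds only for a uniform period shift. For a treatment shift the table above shows clear attenuation, severe when the spread is small.
- **The blind case does not bias the primary comparison.** The model for peak VO₂ has period as a fixed effect, so a shift common to all participants in one period is adjusted for. This stands in full.
- **Wattage is not effort alone.** A drug that improves exercise capacity could raise wattage and peak VO₂ together, so a treatment difference in wattage cannot by itself separate effort from effect. This stands, and it is why the effort indicators must be read with it.
- **The coefficient is not named.** An absolute-agreement intraclass correlation would respond to a shift, but nothing in the text points to that form. Spearman's coefficient is as blind to a uniform shift as Pearson's.
- **The wattage SDs are assumed, and no decision hangs on the result.** Both are true. The 0 to 160 W stages are a recording range, not an observed spread, and the check does not enter the primary model.

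**Conclusion.** The point holds and is minor. An ordinary correlation cannot deliver the stated purpose: it is unaffected by a uniform period shift, which is a matter of algebra, and it is raised by between-participant spread, which is likely here but inferred from the age range. Under a treatment shift of 15 to 20 W it falls from 0.90-0.94 to 0.73-0.88, given a within-participant SD of 10 W and a between-participant SD of 30 to 40 W, without revealing how large the shift is or which way it runs.

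A reader might go further and conclude that an effort difference would pass unseen and be taken for a drug effect, or that the primary estimate is compromised. The SAP does not support that. The descriptive summary could reveal a mean shift, the model adjusts for period, and the wattage check feeds into no estimate. What is affected is how confidently peak VO₂ results can be interpreted.

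**What to change.** In section 4.5.1, replace or supplement the correlation with:

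1. the within-participant difference in peak wattage between periods: mean, SD and 95% limits of agreement;
2. the bezafibrate-placebo difference in peak wattage with its 95% CI, from the same mixed model as peak VO₂.

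State that both will be read beside RER, peak heart rate, Borg score and cause of cessation, since a wattage difference may reflect a drug effect as well as effort. If a coefficient is kept, name it and use one that measures absolute agreement.

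The cost is one extra model and one table on data already collected. The primary analysis does not change.

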4.5.2 Secondary outcomes

MLCL/L4-CL ratio / cardiolipin profile

MLCL/L4-CL ratio will be analysed formally using a mixed linear regression model to compare bezafibrate against placebo, in the same way, using the same methods as the primary analysis of peak VO₂ above.

MLCL/L4-CL ratios will also be summarised descriptively using means and SDs (or medians and IQRs) by treatment and period, and graphical representations of the distributions will be presented by treatment and period.

Cardiolipin profile will be analysed visually by the laboratory team and will not form part of the statistical analysis.

PCr/ATP ratio

PCr/ATP ratio for the second period will be summarised descriptively using a mean and SD (or median and IQR) by treatment and overall, and graphical representations of the distribution will be presented by treatment and overall.

Skeletal muscle oxidative function

Skeletal muscle oxidative function (a panel of quantities to determine function) for the second period will be summarised descriptively using means and SDs (or medians and IQRs) by treatment and overall, and graphical representations of the distribution will be presented by treatment and overall.

Quality of life

Quality of life (QoL) index score, derived from value sets calculated via the responses for each domain of the PedsQL questionnaire, will be analysed formally using a mixed linear regression model to compare bezafibrate against placebo, in the same way, using the same methods as the primary analysis of peak VO_2 above, for participants of each age group and parents/carers separately.

Participants' and parents'/carers' QoL scores for each domain of the questionnaire will also be summarised descriptively using means and SDs (or medians and IQRs) or counts and percentages (where appropriate) by treatment and period, and graphical representations of the distributions will be presented by treatment and period.

Absolute neutrophil count

Absolute neutrophil count will also be analysed formally using a mixed linear regression model to compare bezafibrate against placebo, in the same way, using the same methods as the primary analysis of peak VO_2 ratio above.

Amino acid expression

Plasma arginine and plasma cysteine values will also be analysed formally using mixed linear regression models to compare bezafibrate against placebo, in the same way, using the same methods as the primary analysis of peak VO_2 ratio above.

Cardiac function

Cardiac function is measured by ECHO and MRI. The main ECHO parameters of interest reported at rest, exercise and 2 min recovery are:

- Left ventricular biplane ejection fraction (LVEF %)
- Left ventricular peak systolic mean longitudinal strain (LV PSMLS %)
- Left ventricular peak systolic mean circumferential strain (LV PSMCS %),
- Diastolic ratio (MV E / LV E' cm/s)

The main MRI parameters of interest at rest are:

- LVEF %

- Right ventricular ejection fraction (RVEF %)

All these parameters will be analysed formally using mixed linear regression models to compare bezafibrate against placebo, in the same way, using the same methods as the primary analysis of peak VO_2 above.

Other data collected relating to cardiac function will be summarised descriptively using means and standard deviations (SDs) (or medians and interquartile range (IQR) depending on the distribution) or counts and percentages (where appropriate) by treatment, period and overall and will include:

Cardiac function at rest:

- LV function
 - Fraction shortening (Teichholz) (%)
 - Biplane ejection fraction (%)
 - Myocardial performance index
 - Mitral annular plane systolic excursion (MAPSE) – lateral and septal (mm)
- LV Tissue Doppler
 - S', E' and A' wave velocity (cm/s)
 - IVA (m/s^2)
 - E/E'
 - Mean systolic longitudinal strain (%) and strain rate
 - Lateral basal, mid and apical (%)
 - Septal basal, mid and apical (%)
 - Mean systolic circumferential strain (%) and strain rate
 - Anterior septal, anterior, lateral, posterior, inferior, septal (%)
 - E and A wave velocity (cm/s)
 - Deceleration time (ms)
 - E/A
 - IVS S', E' and A' wave velocity (cm/s)
 - IVS IVA (m/s^2)
 - 3D mean systolic strain
 - Wall motion abnormalities (Yes, No) – including description
- RV function
 - Wall motion abnormalities (Yes, No) – including description
 - TR peak velocity (m/s) (if given)
 - TAPSE (mm)
 - Myocardial performance index
 - Fractional area of change (%)
 - Mean systolic longitudinal strain (%) and strain rate
 - Lateral basal, mid, and apical (%)
- RV Tissue Doppler (pulsed wave)
 - S', E' and A' wave velocity (cm/s)
 - IVA (m/s^2)
 - E/E'
 - E and A wave velocity (cm/s)

Cardiac function during exercise will also be summarised descriptively using means and SDs (or medians and IQRs) or counts and percentages (where appropriate) by treatment, period and overall and will include:

- Exercise history
 - Exercise (hr/week)
 - Self-assessment of exercise capacity (1 = Low, 10 = Elite)

- Motivation (Low, Average, High)
- Exercise test
 - The following will be taken at: baseline (pre-exercise); at 20W increments starting at 0W until 160W; and in recovery (2 and 6 mins post-exercise)
 - Heart rate (bpm)
 - Systolic and diastolic blood pressure (mmHg)
 - Peripheral capillary oxygen saturation (SpO₂) (%)
 - Comments on symptoms and ECG
 - Near-infrared spectroscopy (NIRS) (%)

The following will also form part of the exercise test:

- Exercise duration (m:s)
- Achieved work rate
- Cause and comments on cessation
- Perceived exercise effort – Borg scale at end of exercise (1-10)
- Peak heart rate (bpm)
- Systolic and diastolic blood pressure at rest and peak (mmHg)
- Exercise ECHO
 - The following will be taken at: baseline (pre-exercise); at 20W increments starting at 0W until 160W; and in recovery (2 and 6 mins post-exercise)
 - MV E cm/s
 - LV PSMLS %
 - LV PSMCS %
 - LV S' cm/s
 - LV E' cm/s
 - RV PSMLS %
 - TR m/s
 - RV S' cm/s
 - RV E' cm/s

The following will also form part of the exercise ECHO:

- Anaerobic threshold (%)
- O₂ pulse (ml/beat)
- RER
- METs
- VO₂ measurement at baseline (pre-exercise) and at recovery (2 and 6 mins post-exercise) (ml/kg/min)

Cardiac function by ECG will be summarised descriptively using means and SDs (or medians and IQRs) or counts and percentages (where appropriate) by treatment, period and overall. ECG at rest will include:

- Heart rate (bpm)
- Baseline rhythm, status of the following:
 - Sinus rhythm
 - Heart block
 - Atrial fibrillation/flutter

- Paced
- P wave normal
- P-axis (°)
- PR-interval (ms)
- QRS-axis (°)
- QRS-duration (ms)
- Left ventricular hypertrophy
- Right ventricular hypertrophy
- ST-segments
- ST depression
- TWI
- T axis (°)
- QTc (ms)

ECG during exercise will report new rhythm (sinus rhythm, heart block, atrial fibrillation and pacing occurrence), if changed.

Cardiac MRI data will also be summarised descriptively using line listings, means and SDs (or medians and IQRs) or counts and percentages (where appropriate) by treatment, period and overall, and will include for both left and right ventricular function in turn:

- Existence of wall type abnormalities, and if so, what type and where
- Structure
- Absolute and indexed ventricular function:
 - Ejection fraction (%)
 - End diastolic volume (mL/m²)
 - End systolic volume (mL/m²)
 - Stroke volume (mL)
 - Cardiac output (L/min)
 - Cardiac index (L/min/m²)
 - Mass (g/m²)

Lymphocyte mitochondria

Lymphocyte mitochondria will be summarised descriptively using means and SDs (or medians and IQRs) by treatment, period and overall and will include:

- Mitochondrial size
- Numbers of mitochondria per lymphocyte
- Total area of mitochondria per lymphocyte
- Area of mitochondria as proportion of cytoplasm
- Mitochondria function and cristae organisation in lymphocytes

Arrhythmia profile

Arrhythmia profile will be summarised descriptively using counts and percentages by treatment, period and overall and will include:

- Sinus rhythm (Yes, No) at rest and during exercise

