1.2 Background of study

1.2.1 Summary

Barth syndrome is a rare, life threatening, genetic disease which affects young males. It is caused by abnormal fats (lipids) in the powerhouses of cells (mitochondria) and those who suffer with it often develop heart failure, heart rhythm abnormalities, bacterial infections, poor growth or feeding, weak muscles, developmental delay, severe exercise intolerance, lethargy and fatigue; all of which affect their daily life. Low white blood cell counts occur frequently due to intermittent or persistent reduction in numbers of the neutrophils that are responsible for fighting bacterial infections. This requires expensive and distressing injections to stimulate the bone marrow to produce more neutrophils. In addition, approximately one third of all males living with this disease in the UK have required heart transplantation.

Scientific research has shown that several treatments can improve the fat abnormalities in cells affected by Barth syndrome from either mice or humans; one of which is a drug called bezafibrate. Bezafibrate is particularly attractive as it has been safely administered for over 20 years in the UK to both adults and children for the treatment of high blood fats. The purpose of this study is to see if bezafibrate can be given safely and effectively to people with Barth syndrome in a blinded randomised trial.

Bezafibrate or an inactive (placebo) treatment will be given for 4 months, followed by a one month break, and then followed by 4 months of the alternate treatment (e.g. placebo if bezafibrate taken for the first 4 months and vice versa). Half of the participants will take bezafibrate first, the other half will take placebo first; participants and research staff will not know which order the treatments are given in (double-blind trial).

Once the participants have completed the first phase of treatment, the study statistician will be unblinded to the treatment arms and will then assess whether or not there is evidence of efficacy of bezafibrate for the primary outcome.

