3.3 Analysis populations

3.3.1 Intention-to-treat population

All summaries and analyses of the primary and secondary outcomes will be conducted on the intention-to-treat (ITT) population. The ITT population will consist of all participants and periods, included according to the sequence they were randomised to and the treatment they were randomised in that given period, regardless of whether they are ineligible, prematurely discontinued treatment or are otherwise protocol violators/deviators.

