4.6.2 Baseline data

Baseline characteristics to be summarised descriptively using means and SDs (or medians and IQRs) or counts and percentages (where appropriate) by sequence and overall will include:

- Patient type (transplant, non-transplant)
- Age (and age group: <11 years, 11-15 years, 16+ years)
- Weight (kg), height (cm) and body surface area (BSA) (m²)
- Resting measurements:
 - O₂ saturations (%)
 - Systolic and diastolic blood pressure (mmHg)
 - Heart rate (bpm)
 - Respiratory rate (breaths per min)
- Heart sounds normal
- Pulses regular
- Signs of heart failure:
 - Respiratory distress
 - Hepatomegaly
 - Pulmonary auscultation findings
 - Ascites
 - Pitting oedema
- History of the following in the last 4 months, and whether related to exercise:
 - Fainting
 - Dizziness
 - Palpitations
 - Chest pain or tightness
 - Unexpected decrease in exercise capacity or fitness level

Baseline medication history, including dose, unit and frequency of drugs received, will be summarised descriptively using counts and percentages by sequence and overall and will include:

- Cardiac drug usage:
 - Amlodipine
 - Aspirin
 - Atorvastatin
 - Bisoprolol
 - Captopril
 - Carvedilol
 - Digoxin
 - Enalapril
 - Furosemide
 - Lisinopril
 - Pravastatin
 - Propanolol
 - Ramipril
 - Spironolactone
- General supportive care drug use:
 - Citalopram
 - Folic acid
 - Forceval
 - Gaviscon
 - Glycozade
 - Lactulose
 - Lansoprazole
 - Movical
 - Multivitamins
 - Omeprazole
 - Panothenate
 - Pizotifen
 - Ranitidine
 - Seravit
 - Sertroline
 - Sytron
 - Thiamine
- Transplant-related drugs:
 - Ciclosporin
 - Mycophenolate mofetil (MMF)
 - Prednisolone
 - Sirolimus
 - Tacrolimus
- Infection prophylaxis drugs:
 - Amoxicillin
 - Azithromycin
 - Cotrimoxazole
 - Granulocyte-colony stimulating factor (G-CSF)
 - Penicillin
- Other drugs

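### The cardiac analyses pool native and donor hearts and never use transplant status, so an effect on the Barth heart could be understated and a null result could not be explained

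*SAP*

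**What the plan says.** **Transplanted participants are expected.** SAP section 1.2.1 states that "approximately one third of all males living with this disease in the UK have required heart transplantation". Transplantation is not among the exclusions in section 3.1.2. The baseline tables in section 4.6.2 classify participants as transplant or non-transplant and include a block headed "Transplant-related drugs".

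**The cardiac analyses do not use this.** Section 4.5.2 names the main parameters: echo LVEF, longitudinal strain, circumferential strain and diastolic ratio, and MRI LVEF and RVEF. It then says "All these parameters will be analysed formally using mixed linear regression models to compare bezafibrate against placebo", by the same methods as peak VO₂. That model (section 4.5.1) compares treatments "adjusting for period as a fixed effect (exploring interactions where necessary) and participants as random effects". Section 3.3.1 fixes the population: "All summaries and analyses of the primary and secondary outcomes will be conducted on the intention-to-treat (ITT) population".

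**PCr/ATP.** Under section 4.5.2, "PCr/ATP ratio for the second period will be summarised descriptively", by treatment and overall. Section 4.4.2 explains that it is measured only at the end of the second period.

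Patient type is not a covariate, interaction, subgroup or restriction for any outcome. The reference to exploring interactions names no factor.

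**The concern.** Section 3.1.1 defines the disease by a tafazzin mutation, and the first hypothesis in section 1.2.2 is that bezafibrate works by changing the cardiolipin ratio. A transplanted heart comes from another person. The SAP does not say that it lacks the defect, but for a genetic disease this is a sound inference. In a transplanted participant, echo, cardiac MRI and myocardial PCr/ATP therefore examine an organ without the target abnormality.

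The random participant effect removes differences in level between people. It does not stop the treatment effect being averaged over two kinds of heart. If the pooled cardiac estimate is close to zero, the planned output cannot tell whether bezafibrate does nothing for the Barth heart or whether an effect there was averaged with hearts that could not show it.

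PCr/ATP has a further weakness. Each participant contributes one value, under one treatment, so the crossover does not balance heart type between treatments.

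**Working it through.** **Inputs from the SAP.** About one third of UK patients transplanted (1.2.1). "A total of 18 males aged between six and 24 years currently attend the service", of whom 12 to 15 are expected to take part (2.4). Two-sided 5% (2.4).

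**Assumptions, not in the SAP.** f = transplanted share of participants. r = drug effect in donor hearts relative to native hearts. d = native-heart effect in SDs of the paired difference, with that SD equal in both heart types.

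**1. The plan's own figure.** The SAP gives no power for cardiac outcomes. For peak VO₂ with n = 12 it gives 0.90 SD at 80% and 1.05 SD at 90%. A noncentral t calculation with noncentrality d√n and n − 2 = 10 degrees of freedom gives 80.2% and 90.5%. The method thus reproduces the plan when d is in SDs of the within-subject difference, and that unit is used below. (Section 2.4 labels the unit as within-subject SDs. Read literally, power would be about 51% and 64%. That is a separate matter.)

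**2. Dilution.** Pooled effect ÷ native-heart effect = 1 − f(1 − r).

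| f | r | Ratio |
|---|---|---|
| 1/6 | 0 | 0.83 |
| 1/4 | 0 | 0.75 |
| 1/3 | 0 | 0.67 |
| 1/2 | 0 | 0.50 |
| 1/3 | 0.25 | 0.75 |
| 1/3 | 0.5 | 0.83 |
| 1/3 | 1 | 1.00 |

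**3. Range of f.** Assume 6 of the 18 attending patients are transplanted.
- n = 12 could include 0 to 6 of them (f = 0 to 50%; expected 4).
- n = 15 could include 3 to 6 (f = 20 to 40%; expected 5).

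With r = 0 the shortfall equals f: 0–50% at n = 12 and 20–40% at n = 15. If consent is unrelated to transplant status, 3 to 5 transplanted among 12 has probability 0.237 + 0.400 + 0.256 = 0.893, so the ends of the n = 12 range are unlikely.

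**4. Power, pooled against native hearts only.** Take d = 1.0 and f = 1/3. The pooled SD of the paired difference is √(1 + f(1 − f)(1 − r)²d²), with n − 2 degrees of freedom. For r = 0 the pooled effect is 0.667/√(1 + 2/9) = 0.667/1.106 = 0.603 SD.

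| r | n = 12 pooled | 8 native | n = 15 pooled | 10 native |
|---|---|---|---|---|
| 0 | 47% | 66% | 58% | 79% |
| 0.25 | 60% | 66% | 72% | 79% |
| 0.5 | 72% | 66% | 83% | 79% |
| 1 | 88% | 66% | 95% | 79% |

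Restriction gains power when donor hearts respond little, and loses it once they respond about half as much as native hearts.

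**5. PCr/ATP.** With 4 donor hearts among 12 participants split 6/6, P(2–2) = C(4,2)·C(8,4)/C(12,6) = 6 × 70/924 = 0.455. P(3–1 or 4–0, either way) = 1 − 0.455 = 0.545, about 55%. A summary by treatment and overall would not reveal the imbalance.

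**The case against.** The strongest reply is that the size of the problem is unknown and may be small.

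- **Share.** A reader might infer that cardiac effects are diluted by a third as a matter of fact. The documents do not support that. One third describes UK patients, not participants, and the renal, shortening-fraction, arrhythmia and stability criteria could move the enrolled share either way. This stands, and is why a range is given.
- **Donor response.** A reader might infer that a donor heart cannot respond. That follows only for the cardiolipin route. Section 1.2.2 also allows benefit independent of cardiolipin, and exercise echo is taken during whole-body effort, so an indirect effect is not excluded. This stands too. That hypothesis speaks of mitochondrial pathologies, however, so it does not show that donor hearts respond.
- **Power.** A reader might infer that restricting to native hearts always gains power. The working shows that this depends on r.
- **Estimand.** The pooled model validly estimates the average effect in those enrolled, and section 3.3.1 declares ITT. Replacing it with a subset of about 8–10 would be a debatable choice. This stands, and the fix keeps ITT.
- **Impact.** These are secondary outcomes, to be read for consistency, magnitude and direction (4.1). PCr/ATP is descriptive only, and cardiac MRI already gets line listings, though not stated to be by patient type.

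None of this supplies an analysis that isolates the native heart.

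**Conclusion.** The concern holds as a gap in interpretation with a conditional size. The SAP expects transplanted participants and records who they are, but every formal echo and MRI model and the PCr/ATP summary pool the two heart types. The pooled effect would be about one third below the native-heart effect if f = 1/3 and donor hearts do not respond. It would be 0–50% (n = 12) or 20–40% (n = 15) below if 6 of 18 attending patients are transplanted and donor hearts do not respond, and less far below with partial response. All of this rests on the inference that a donor heart lacks the defect. If any transplanted participants enrol, a null pooled result could not separate no effect on Barth hearts from dilution. For PCr/ATP, an imbalance in heart type between treatments is more likely than not in the 4-of-12 illustration. The primary outcome is not in question. This is a cheap improvement that should be made before analysis, not a fault that invalidates the trial.

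**What to change.** In section 4.5.2:

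1. Keep the ITT cardiac models as written.
2. Pre-specify beside them the same models in non-transplant participants, for echo LVEF, both strains and diastolic ratio, and for MRI LVEF and RVEF. Report estimates with 95% confidence intervals.
3. List the cardiac results of transplanted participants separately.
4. Present PCr/ATP by patient type within treatment, with the number of each type shown.
5. State that the native-heart results are there to interpret the pooled ones, and that no gain in power is claimed.

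The cost is a few lines of SAP text and one extra model run per cardiac parameter. Patient type is a baseline variable already collected, so selecting on it keeps the randomised comparison, and fixing it now avoids a post hoc subgroup. The downside is that native-heart estimates rest on about 8–10 participants if one third are transplanted, so intervals will be wide, and the number of secondary tests rises with no multiplicity adjustment.
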